5.5.2. Analysis Methods

Unless otherwise specified, the exploratory endpoints listed and defined in Section 5.5.1 will be analyzed based on the FAS according to the randomized intervention group regardless of the intervention actually received.

All exploratory endpoints will be tested regardless of the significance of the primary and secondary endpoints; the testing of these endpoints will not be controlled for multiplicity. Nominal p-values will be presented.

Descriptive statistics (ie, N, mean, median, SD, IQ range, minimum, and maximum) will be used to summarize continuous variables. Frequency counts and percentages will be used to summarize categorical variables. Graphical data displays (eg, line plots) may also be used to summarize the data.

Binary Endpoints

The intercurrent events captured for binary endpoints specified in Section 5.3.2 will be applied to each of the above binary endpoints. Participants with ICEs in categories 1-4 will be considered to have unfavored outcome. For participants experiencing an ICE 5 and ICE 6, their observed values will be used, if available.

Participants with any missing data for an endpoint after accounting for the ICEs will be imputed as having unfavored outcome. Binary endpoints will be summarized with the number and frequency of participants who achieve the endpoint by treatment group. Treatment comparisons will be performed using CMH chi-square test stratified by clinical remission status at baseline (CDAI < 150, CDAI \ge 150), region (North America, Western Europe, rest of world) and number of prior surgeries (1 surgery versus > 1 surgery, with the qualifying surgery counting as 1 surgery). In case of rare events, the Fisher's exact test will be used for treatment comparisons.

Time-to-event Endpoints

The ICEs captured for time-to-event endpoints specified in Section 5.4.1 will be applied to each of the above time-to-event endpoints. Participants with ICEs in categories 1-3 will be considered to have unfavored outcome. For participants experiencing an ICE 4 and ICE 5, their observed values will be used, if available.

Time-to-event endpoints will be summarized with median survival time and interquartile range of survival time by treatment group. Kaplan-Meier curves will be provided for time-to-event endpoints as well. Treatment comparisons will be performed using the log-rank test stratified by clinical remission status at baseline (CDAI < 150, CDAI \ge 150), region (North America, Western Europe, rest of world) and number of prior surgeries (1 surgery versus > 1 surgery, with the qualifying surgery counting as 1 surgery).

Continuous Endpoints

The ICEs specified as following will be applied to each of the above continuous endpoints, ie, if a participant has an ICE in categories 1-4, last available values will be assigned from the point of ICE onward (i.e., no change from baseline). For participants experiencing an ICE 5 or ICE 6, their observed values will be used, if available. Note that the application of ICE categories 1-4 overrides that of ICE 6 and ICE 6. This means that for a participant with an ICE in categories 1-4 baseline values will be assigned from the point of ICE onward (ie, no change from baseline), regardless of whether the participant has had an ICE 5 or ICE 6.

To account for the missing data for continuous endpoints of change from baseline measured at more than one post-baseline visit (after applying the ICEs), a Mixed-Effect Model Repeated Measures (MMRM) will be used, under the assumption of missing at random (MAR), to test the difference between treatment groups. In MMRM, missing data will not be imputed, but rather missing data will be accounted for through correlation of repeated measures in the model. Additionally, if the MMRM normality assumption is in question, an appropriate transformation may be implemented before fitting the MMRM model.

The explanatory variables of the MMRM model will include treatment group, visit, applicable baseline score, clinical remission status at baseline (CDAI < 150, CDAI \ge 150), region (North America, Western Europe, rest of world) and number of prior surgeries (1 surgery versus > 1 surgery, with the qualifying surgery counting as 1 surgery), an interaction term of visit with treatment group, and an interaction term of visit with applicable baseline score.

An unstructured covariance matrix for repeated measures within a participant will be used. The F test will use Kenward-Roger's approximation for degree of freedom. In case of lack of convergence, empirical structured covariances will be used in the following order until convergence is reached: 1) Toeplitz, 2) first order Autoregressive Moving Average.

The treatment difference between treatment groups will be estimated by the difference in the least squares means (LSmeans). The 95% 2-sided CI for the differences in LSmeans and p-values will be calculated based on the MMRM.

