A Week 48 video ileocolonoscopy will be performed between Weeks 48 and 51 and participants with endoscopic recurrence confirmed by a central reader will cross over to open-label treatment with guselkumab SC induction. An optional video ileocolonoscopy can be performed at Week 24 and cross over will occur at the discretion of the principal investigator if there is only endoscopic recurrence without disease recurrence. If participants meet criteria for disease recurrence after Week 8 they will also cross over to open-label treatment.

Participants who discontinue study intervention early will return for an early termination visit at least 12 weeks after study intervention discontinuation, which will also serve as their final safety visit. This visit will include a video ileocolonoscopy at the time of discontinuation, except those participants who have already had demonstrated endoscopic recurrence in a study ileocolonoscopy.

Database Locks and Maintenance of the Blind

The first database lock (DBL) is the main study DBL. It will occur when all participants have completed the Week 48 visit assessments, or have terminated study participation prior to Week 48, and will include all assessments performed as of that date (even those beyond Week 48). The final DBL will occur after the last participant completes the final safety visit at Week 156. Additional DBLs may be added between Weeks 48 and 156, as warranted.

The study blind will be maintained for the investigative sites, site monitors, and study participants until after the final participant has completed their Week 156 visit. In the event of an emergency, the investigator may also unblind a participant's treatment if such knowledge would change the participants' clinical care. The sponsor will remain blinded to the original treatment assignments until after the main study DBL has occurred.

Study Length

After the screening period, the total study duration is 156 weeks, with the final dose of study intervention given at Week 144 and the final efficacy visit at Week 152 followed by the final safety visit at Week 156. The end of the study is defined as when all participants have completed the Week 156 visit assessments, or have terminated study participation prior to Week 156 and had their last follow-up assessment (12 weeks after the last dose of study intervention or at early termination visit).

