5.3.2. Estimand

5.3.2.1. Primary Estimand

An estimand is a precise definition of the primary targeted treatment effect defined by the following 5 attributes: Study Intervention, population, variable (endpoint), intercurrent events (ICEs) and corresponding strategies, and population-level summary.

Primary Trial Objective: To evaluate the efficacy of guselkumab treatment prior to or at Week 48 compared with placebo in preventing endoscopic recurrence of CD in participants after surgery.

Estimand Scientific Question of Interest: What is the proportion of participants developing endoscopic recurrence prior to or at Week 48, and thus considered to have benefited from guselkumab versus placebo?

Study intervention:

- Experimental: Guselkumab ^{CCI} at Week 0 and then ^{CCI} at Week 8, then ^{CCI} thereafter through the end of the total study period.
- Control: Matched placebo CCI at Weeks 0 and 8 and then CCI thereafter through the end of the total study period.

Population: Participants with recent (<49 days) qualifying surgery and no evidence of active Crohn's disease postoperatively.

Variable: A binary recurrence variable (recurrence/no recurrence) where recurrence is defined as Endoscopic Recurrence prior to or at Week 48 (as defined by modified Rutgeerts score greater than or equal to i2a in the neo-terminal ileum, anastomotic site, or its equivalent elsewhere in the GI tract (eg, colonic ulceration)) or experiencing intercurrent events (ICEs) 1-4 presented below.

Summary Measure (Population-level summary): Difference in proportions of the binary recurrence variable of endoscopic recurrence, as described above, between guselkumab group and the placebo group.

Intercurrent events and their corresponding strategies:

The ICEs considered for this study are listed in Table 7:

Table 7:	Intercurrent Events and Corresponding Analysis Strategies for Endoscopic Recurrence prior to
	or at Week 48

Inte	ercurrent Events (between baseline and Week 48)	Analysis Strategy for Intercurrent Events
1. 2.	A CD-related surgery (with the exception of minor procedures such as drainage of a superficial abscess or seton placement, etc.) A prohibited change in CD medication	
3. 4.	Discontinuation of study intervention due to lack of efficacy or an AE of worsening CD Cross over to open-label guselkumab	

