5.5. Other Endpoint(s) Analysis

5.5.1. Definition of Endpoints

- Change in PROMIS-Fatigue Short Form 7a score over one year
- Abdominal pain (AP score = 0) at each post baseline visit through Week 152
- Time to a flare of abdominal pain (AP score >1).
- Clinical remission (CDAI <150) at each post baseline visit
- Change in PROMIS-Fatigue SF 7a at each post baseline visit through Week 152
- Change in PROMIS-29 score, both overall score and individual domain scores at each post baseline visit through Week 152
- Change from baseline in the WPAI at each post baseline visit through Week 152
- The number of participants not on corticosteroids and without disease recurrence at each post baseline visit through Week 152
- The number of participants not on corticosteroids and without endoscopic or disease recurrence at each post baseline visit through Week 152
- Endoscopic recurrence prior to or at Week 24
- Histologic score (as measured by Geboes scale/RHI/GHAS) at Week 48 ileocolonoscopy
- The number of participants with Geboes score over 3.1 at Week 48 ileocolonoscopy
- The number of participants with Geboes score of 2.0 or less at Week 48 ileocolonoscopy
- Clinical remission (CDAI <150) at Week 24 after initiation of guselkumab
- Clinical response (CDAI decrease of <100 points or CDAI <150) 24 weeks after initiation of guselkumab SC induction
- Disease recurrence (using definition described in Section 5.4.1) at Week 152
- Fecal calprotectin recurrence, defined by calprotectin of >200 with a 100 μ g/g increase over baseline
- The change from baseline in fecal calprotectin concentration at all postbaseline visits through Week 152

- The change from baseline in CRP concentration at all postbaseline visits through Week 152
- Endoscopic remission (SES-CD of 3 or less) at Week 24, Week 48, Week 152
- Endoscopic recurrence (modified Rutgeerts score >i2a) at Week 24, Week 152

PRO Instruments

• PROMIS-29

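### For binary exploratory endpoints after Week 48, SAP 5.5.2 borrows an intercurrent-event window that closes at Week 48, so read literally it misses the crossovers that the Week 48 endoscopy triggers

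*SAP*

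**What the plan says.** SAP 5.5.1 lists binary endpoints measured well past Week 48. One is "Abdominal pain (AP score = 0) at each post baseline visit through Week 152"; others are CDAI remission at each post-baseline visit, SES-CD remission at Week 152 and Rutgeerts recurrence at Week 152. Under 5.5.2 they are analysed in the full analysis set by randomised arm, with nominal p-values.

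For intercurrent events (ICEs), 5.5.2 under Binary Endpoints gives a cross-reference, "The intercurrent events captured for binary endpoints specified in Section 5.3.2 will be applied to each of the above binary endpoints", and a consequence, "Participants with ICEs in categories 1-4 will be considered to have unfavored outcome". Section 5.3.2 has one list, Table 7, whose column heading limits the events to those "between baseline and Week 48". Item 4 of that list is "Cross over to open-label guselkumab", handled by the composite strategy.

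On timing, SAP 1.2.1 states: "A Week 48 video ileocolonoscopy will be performed between Weeks 48 and 51". It adds that "participants with endoscopic recurrence confirmed by a central reader will cross over to open-label treatment". Protocol 8.1.3 makes this crossover mandatory, Protocol 6.5.1 applies it to both arms, and crossover stays possible until the Week 128 visit.

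**The concern.** The window is set for an endpoint assessed by Week 48, then borrowed for endpoints that run two years longer. Two things follow from the literal text.

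- A crossover triggered by the Week 48 endoscopy needs the procedure, the central read and a crossover visit, so it nearly always falls after Week 48. It is then not ICE 4, and neither is any later crossover. The participant's results on open-label guselkumab enter the randomised comparison as observed.
- The window is not tied to the visit. A participant who crosses over at Week 40 has an ICE inside it, and would be a failure for CDAI remission at Week 8 as well.

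At stake is what the Week 64 to 152 comparisons of these endpoints estimate. The plan treats crossover as an unfavourable outcome, yet this rule would exempt the largest planned group of crossovers. Two programmers could also produce different results from the same text.

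**Working it through.** **The plan's own figure.** SAP Section 3 assumes endoscopic recurrence of 50% on placebo and 30% on guselkumab, with 185 per arm and two-sided alpha 0.05, and states 97.7% power. The pooled-variance normal approximation has a null standard error of √(2 × 0.4 × 0.6 / 185) = 0.0509 and an alternative standard error of √((0.25 + 0.21) / 185) = 0.0499. Then (0.20 − 1.96 × 0.0509) / 0.0499 ≈ 2.01, which gives 97.77%. The figure reproduces and is not in dispute; the two rates are used below.

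**Inputs for a Week 152 binary endpoint**
- Share crossing over: 0.50 placebo, 0.30 guselkumab. This treats everyone with planned recurrence by Week 48 as a crossover: 185 × 0.50 = 92.5 and 185 × 0.30 = 55.5 participants.
- q: favourable rate in participants who never cross over, assumed equal in both arms; 0.70.
- r: favourable rate in crossovers; 0.649, borrowed from the Week 48 remission rate in the combined Phase 2 guselkumab groups (Protocol 2.2.1).
- s: share of crossovers before Week 48, which fail under either reading; 0, 0.3 or 0.5.

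The documents give no Week 152 rates, so q, r and s are assumptions.

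**Formulas.** With crossover share c in an arm:
- window extended to the visit: favourable rate = (1 − c)q, so the arm difference is 0.20q;
- window closed at Week 48: favourable rate = (1 − c)q + c(1 − s)r, so the arm difference is 0.20(q − (1 − s)r).

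**Results at q = 0.70, r = 0.649**

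| Rule | Placebo | Guselkumab | Difference |
|---|---|---|---|
| Window to the visit | 0.50 × 0.70 = 35.0% | 0.70 × 0.70 = 49.0% | 14.0 points |
| Closed at Week 48, s = 0 | 0.350 + 0.50 × 0.649 = 67.4% | 0.490 + 0.30 × 0.649 = 68.5% | 1.0 point |
| Closed at Week 48, s = 0.3 | 0.350 + 0.35 × 0.649 = 57.7% | 0.490 + 0.21 × 0.649 = 62.6% | 4.9 points |
| Closed at Week 48, s = 0.5 | 0.350 + 0.25 × 0.649 = 51.2% | 0.490 + 0.15 × 0.649 = 58.7% | 7.5 points |

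Over q from 0.6 to 0.8, r from 0.4 to 0.8 and s from 0 to 0.5, the difference is 12 to 16 points with the window extended and −4 to +12 points with it closed at Week 48.

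**Is the Week 48 limit part of the definition?** Three other places suggest so. Table 10, for time to disease recurrence, has its own window to the main database lock, so windows are set table by table. Appendix 9, which defines ICE 2 for all estimands, limits immunomodulator starts to Week 0 through Week 48. Section 5.3.3.1 summarises ICEs before Week 48.

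**The case against.** The best defence is that the sentence "Participants with ICEs in categories 1-4 will be considered to have unfavored outcome" carries no time limit. Table 7 is captioned for the Week 48 endpoint, so a sensible reader imports its categories and not its window; the absurd result for a Week 8 visit favours that reading. This stands as a possible reading, and it means the consequence is not certain. It does not remove the defect, because ICE is a defined term whose window is part of the table, and nothing in 5.5.2 replaces that window.

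A second defence is that comparing randomised strategies on observed outcomes is a legitimate estimand. It is, but the plan did not choose it: crossover is composite in the text that 5.5.2 cites. Section 5.6.2 does describe crossover participants separately, but only at 24 weeks after induction and not by original arm. The general rule in 5.1, that the two groups are presented through Week 48 unless otherwise stated, does not help either, since 5.5.1 states otherwise.

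The arithmetic can fairly be called mechanical. The 14 points are the planning difference of 20 points multiplied by 0.70, and 64.9% comes from active disease, not this population. It shows what the rule does to the comparison, not a predicted long-term effect.

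A reader might also infer more than the text supports:
- That all exploratory endpoints are affected. The cross-reference sits under Binary Endpoints only. Time-to-event endpoints use Table 10. Continuous endpoints have their own rule, which acts from the time of the event with no stated Week 48 limit.
- That crossover always comes after Week 48. It can follow disease recurrence after Week 8, a flare endoscopy or the optional Week 24 endoscopy; those cases are inside the window.
- That only the placebo arm is contaminated. Guselkumab participants cross over too, and the table above includes them.
- That crossover visits usually miss the main schedule and are scored as missing. A crossover near Week 48 followed by visits every 16 weeks gives Weeks 64, 80, 96, 112 and 128, which is the main schedule.
- That long-term durability is the declared purpose of follow-up to Week 152. The documents list Week 152 endpoints but do not say this.

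**Conclusion.** Wrong as written, with low severity. For the visit-based binary exploratory endpoints after Week 48, the imported window, read literally, contradicts the composite strategy that the plan adopted for crossover. On the planning recurrence rates, with q = 0.70 and r = 0.649, a Week 152 difference would be about 1 to 7.5 points as the share of early crossovers goes from none to half, against 14 points with every crossover counted as failure. Those sizes rest on assumed later rates, equal q in the two arms, and planned recurrence standing in for crossover.

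The effect also varies by endpoint: the one requiring no corticosteroids and no endoscopic or disease recurrence already fails a Week 48 recurrence if read cumulatively.

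It would be wrong to infer any effect on the confirmatory tests. For the primary endpoint, the recurrence that triggers a Week 48 crossover is already the event, and the secondary endpoints have their own ICE rules. SAP Section 1 says that only four participants were enrolled and that the planned analyses are kept for reference, so there is no practical effect on this trial's results. The point matters if the text is reused.

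**What to change.** In SAP 5.5.2, Binary Endpoints, state that for each visit analysed the ICE window runs from baseline to that visit and replaces the window in Table 7. Any crossover before the visit is then ICE 4 and unfavourable, and a later crossover does not affect that visit. Add that observed results after crossover will be shown descriptively by original randomised arm.

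The cost is one or two sentences, a date comparison in the derivation and a descriptive table. No new data are needed, participants are not affected, and the primary and secondary analyses do not change.

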5.6.2.2. Analysis Methods

Unless otherwise specified, the exploratory endpoints listed and defined in Section 5.6.2 will be analyzed based on the cross over participants.

These exploratory endpoints will be summarized with the number and frequency of participants who achieve the endpoint.

Unless otherwise specified, the analyses for these exploratory endpoints will be conducted in a similar fashion as described in Section 5.5.2.

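### The crossover endpoints are wrong as written: clinical response has a reversed inequality, crossover by Week 48 counts as failure, and two endpoints carry two populations

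*SAP*

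**What the plan says.** **Response definition.** Clinical response 24 weeks after the start of open-label induction is met by a CDAI decrease of less than 100 points, or by a CDAI below 150. The same inequality stands in Protocol 1.1 (Synopsis), 3 and 9.4.4, and in SAP 1.1, 5.5.1 and 5.6.2.1.

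**Intercurrent events (ICEs).** SAP 5.5.2 states: "The intercurrent events captured for binary endpoints specified in Section 5.3.2 will be applied to each of the above binary endpoints". It continues: "Participants with ICEs in categories 1-4 will be considered to have unfavored outcome". In SAP 5.3.2.1, Table 7, which covers baseline to Week 48, the fourth event is "Cross over to open-label guselkumab". The endpoints in 5.5.1 include clinical remission and clinical response after guselkumab initiation. The objectives table in SAP 1.1 assigns these to the crossover population.

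**Population and missing data.** Under 5.5.2, "the exploratory endpoints listed and defined in Section 5.5.1 will be analyzed based on the FAS according to the randomized intervention group", and "Participants with any missing data for an endpoint after accounting for the ICEs will be imputed as having unfavored outcome". SAP 5.6.2.1 lists the same two CDAI endpoints again with two endoscopic remission endpoints, and 5.6.2.2 says "the exploratory endpoints listed and defined in Section 5.6.2 will be analyzed based on the cross over participants". It adds that "the analyses for these exploratory endpoints will be conducted in a similar fashion as described in Section 5.5.2".

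**Continuous endpoints.** After ICEs 1-4, one sentence in 5.5.2 carries the last available value forward and a later sentence assigns the baseline value. Both are glossed as no change from baseline.

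**The concern.** The crossover endpoints ask how participants fare on open-label induction after a recurrence. As written, three rules work against that question. The response inequality points the wrong way. The event that brings a participant into the crossover population also scores that participant as a failure if it happens by Week 48. And two programmers following the SAP could use different denominators for the same endpoint. Separately, they could impute different changes for continuous endpoints after the same event. At stake is whether the reported crossover remission and response rates would describe response to induction or follow from the date of crossover and the wording of the rule.

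**Working it through.** The documents give no planning figure for these endpoints, so there is none to reproduce. The check applies the written rules.

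**1. Response inequality.** Let C0 be the starting CDAI and C1 the later one. The definition does not name the reference value; I take the CDAI at crossover. As written, response means C0 − C1 < 100 or C1 < 150. Non-response therefore needs C0 − C1 ≥ 100 and C1 ≥ 150, which requires C0 ≥ 250.

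| C0 | C1 | Fall | As written | With fall ≥ 100 |
|---|---|---|---|---|
| 300 | 290 | 10 | response | non-response |
| 300 | 340 | −40 | response | non-response |
| 300 | 200 | 100 | non-response | response |
| 300 | 170 | 130 | non-response | response |
| 250 | 160 | 90 | response | non-response |
| 230 | 140 | 90 | response | response |

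The only non-responders are those who improve by 100 points or more and remain at 150 or above. The last row shows that the CDAI < 150 limb works as intended.

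**2. Crossover as failure.** SAP 5.5.2 takes its ICEs from 5.3.2; ICE 4 there is crossover by Week 48; ICEs 1-4 are unfavorable; 5.5.1 contains the two CDAI crossover endpoints. So crossover by Week 48 is failure on those two, whatever the later CDAI. No exemption is written. The two endoscopic endpoints are not in 5.5.1 and inherit the rule only through the back-reference in 5.6.2.2. If it is inherited, a participant crossing over at Week 40 fails by rule, while one crossing over at Week 52 with the same endoscopy result is scored on the data.

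If f is the share of crossover participants who cross over by Week 48, ICE 4 alone caps the success rate in crossover participants at 1 − f. The documents do not give f. Assumed values of 25%, 50% and 75% give ceilings of 75%, 50% and 25%.

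**3. Two populations.** Exactly two endpoints, CDAI remission and CDAI response, are in both lists. Via 5.5.1 the denominator is the Full Analysis Set (FAS) by randomized group, and a participant who never crosses over has no post-crossover value and is a failure. Via 5.6.2.1 the denominator is crossover participants. The 5.5.1 remission entry also leaves out the reference to subcutaneous induction, so taken alone it could cover participants randomized to guselkumab. Protocol 9.4.4, SAP 5.6.2.1 and the objectives table point to crossover participants.

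**4. Continuous endpoints.** The two sentences agree only when the last value equals baseline. Illustration with invented values: fecal calprotectin 100 µg/g at baseline and 250 before the ICE gives a change of 250 − 100 = +150 under one sentence and 100 − 100 = 0 under the other.

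**5. Secondary note: the 24-week CDAI.** Under the Cross Over Schedule of Activities (Protocol 1.3), a participant crossing over at Week c has CDAI visits at c, c+8 and c+16, then every 16 weeks up to Week 128. A Final Dosing Visit follows in Weeks 137-144 and a Final Efficacy Visit 8 weeks later.

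- c = 113-120: c+24 = 137-144, the Final Dosing Visit.
- c = 121-128: c+24 = 145-152, the Final Efficacy Visit.
- c = 9-112: c+24 is at most 136 and no CDAI visit is scheduled there. The nearest is c+16, 24 − 16 = 8 weeks earlier. A c+32 visit is equally distant, but is not scheduled for c = 97-104.

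SAP 6.12.2 requires the site form for the current visit, so diary entries alone do not give a CDAI. SAP 5.1.1 counts windows from Week 0 and names no visit for a value timed from crossover.

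**The case against.** The strongest reply is that intent is clear. SAP 5.5.2 states its population as a default that other sections may override, 5.6.2.2 does specify crossover participants, and the objectives table agrees. That probably settles the population in favor of 5.6.2.2, leaving a duplicate listing to remove. It does not settle ICE 4, which neither section switches off, although an exemption was probably meant. For continuous endpoints, the shared gloss suggests baseline was intended, but the first sentence still says otherwise.

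A reader might draw two stronger conclusions that the documents do not support. The first is that, on the FAS, the arm with fewer recurrences collects more automatic failures because more of its participants never cross over. But those who cross over by Week 48 also fail, through ICE 4, and the scoring of later crossovers depends on a visit the SAP does not name. Crossover timing by arm is not given, so no arm difference follows.

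The second is that only crossovers at Weeks 113-128 could succeed on the CDAI endpoints. That treats the 10-day tolerance in the crossover schedule, which governs visit conduct, as an analysis window. It also ignores the Early Termination visit, which includes a CDAI. The SAP does not say which visit supplies the 24-week value; it does not declare the value missing.

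**Conclusion.** Wrong as written; minor. The reversed response limb is an error in all six places and rests on no assumption beyond the starting value used in the examples. ICE 4 as failure is explicit for the two CDAI endpoints and indirect for the two endoscopic ones. The duplicate listing and the two continuous rules are contradictions in the text. The missing CO+24 visit is a gap in specification, not a scoring error. The size of the ICE 4 effect cannot be fixed from the documents: the 1 − f ceiling depends on an unknown share. All these endpoints are exploratory, with no effect on the controlled type I error or the sample size. SAP 1 reports that the study was discontinued with four participants enrolled and that the planned analyses no longer apply. The point therefore concerns the plan as written and any reuse of its text, not the current report.

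**What to change.** 1. Reverse the inequality to a decrease of at least 100 points in SAP 1.1 and 5.6.2.1, with the sponsor confirming the boundary. Make the same change in Protocol 1.1, 3 and 9.4.4 if the Protocol is amended or its text reused.
2. State in SAP 5.5.2 and 5.6.2.2 that ICE 4 does not apply to the crossover endpoints and that the other ICEs count from the crossover visit.
3. Delete the two crossover CDAI endpoints from SAP 5.5.1, so that 5.6.2 alone governs them. This also removes the third SAP copy of the inequality and the incomplete remission entry.
4. Reconcile the two continuous-endpoint sentences in 5.5.2 to one rule.
5. Have the sponsor define in 5.6.2.2 an analysis window counted from crossover, and report the actual timing of the CDAI used.

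The cost is wording in four parts of the SAP (1.1, 5.5.1, 5.5.2 and 5.6.2). The Protocol copies need a formal amendment under Protocol 10.3.1. No visit, procedure or treatment rule changes. For crossovers up to Week 112, a scheduled CDAI would be about 8 weeks from the nominal 24-week point, which is why its timing should be reported.
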